9 MEASUREMENTS OF TREATMENT COMPLIANCE

Percent compliance will be calculated as 100 times the doses administered divided by the number of days on treatment. Doses administered will be calculated as the total number of vials dispensed minus the total number of vials returned unused during the study period. Number of days on treatment is calculated as (last dose date – first dose date +1). Drug accountability information, first dose date, last dose date, and study medication interruptions are reported in the eCRF. Subjects will be considered compliant overall for study medication if the calculated compliance is $\geq 80\%$. Overall treatment compliance will be presented for both percent compliance calculations using descriptive statistics and the number and percentage of subjects who are $\geq 80\%$ compliant for both the ITT and Safety Populations. Treatment compliance by visit will not be calculated. Compliance for Stage 2 Only will also be calculated.

Information about interruptions of study medication (start date of interruption, date study medication resumed, and reason for interruption) is included in data listings.

10 EFFICACY/PHARMACODYNAMIC EVALUATION

11.1 Analysis of Efficacy and Pharmacodynamic Variables

All efficacy/pharmacodynamic analyses will be conducted on the ITT and PP populations. Analyses on weekly PN/IV support are based on two data sources: the subject diary data (also referred to as actual data) and the investigator prescribed data.

Investigator prescribed data is captured in the PN history and adjustments eCRFs. The actual weekly PN volume will be calculated based on the daily volumes recorded in subjects' diaries within 14 days prior to each scheduled visit. The calculation will follow the formula below.

$$\text{Weekly value} = (\text{sum of daily values in the diary/number of days with values}) * 7$$

Missing daily PN volumes will not be imputed. If there are more than 5 days of missing diary data within an interval, the interval will be classified as missing actual volume information. An exception to this rule is the Baseline visit, which case traced back beyond 14 days prior to

first dose until 9 data points were obtained. Data will be summarized at all scheduled visits. An End of Treatment (EOT) time point will also be added. Therefore,

- PN/IV volume/ calories and days per week of PN/IV support will be summarized at Baseline, Stage 2 Weeks 2, 4, 8, 12, 16, 20, 24, and nominal visits in Stage 3 and Stage 4 will be summarized.
- Plasma citrulline will be summarized at Baseline, Stage 2 Weeks 4, 8, 16, 24, and nominal visits in Stage 3 and Stage 4 will be summarized.

Data collected at unscheduled time points will be included in the listings but will not be summarized at those unscheduled time points.

Change in weekly PN/IV volume from baseline

The absolute and percent change in weekly PN/IV volume from baseline to each scheduled visit, as well as at EOT, will be presented using descriptive statistics defined in Section 6.1. The 95% confidence intervals will be presented for Week 24 and End of Stage 2.

Response to Teduglutide

The number and percentage of subjects who demonstrate a response at Week 20 and again at Week 24 will be presented. A response is defined as the achievement of at least a 20% reduction from baseline (Visit 2) in weekly PN/I.V. volume.

Binary response to Teduglutide

The number and percentage of subjects who demonstrate a response at each visit will be presented. A response is defined as the achievement of at least a 20% reduction from baseline (Visit 2) in weekly PN/I.V. volume.

Change in days per week of PN/IV support from baseline

The absolute change in days per week of PN/IV support from baseline to each scheduled visit, as well as at EOT, will be presented using descriptive statistics defined in Section 6.1.

Changes in plasma citrulline from baseline

The absolute and percent change in plasma citrulline from baseline to each scheduled visit, as well as at EOT, will be presented using descriptive statistics defined in Section 6.1.

Number of subjects who are able to completely wean off PN/IV support

A subject will be considered to have achieved independence from PN/IV (completely weaned off PN) if the investigator prescribes no PN and there is no use of PN recorded in the subject diary at the last dosing visit.

The number and percentage of subjects who completely wean off PN/IV support up to Week 24 in Stage 2 will be presented. Also, similar analysis will be done for those completely wean off PN/IV support at end of Stage 3 and end of study.

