2.2 Objective

The objectives of this clinical study are to evaluate the safety, efficacy and pharmacokinetics of teduglutide in Japanese subjects with PN/I.V.-dependent SBS over a 24-week period (Stage 2) followed by a long-term extension (Stages 3 and 4) to evaluate safety and continued efficacy.

2.2.1 Efficacy and Pharmacodynamic Endpoints - Stage 2

The efficacy endpoints are as follows:

- Absolute and percent change from baseline in weekly PN/I.V. volume over 24 weeks (by visits and at end of treatment [EOT]). Weekly PN/I.V. volume will be based on the subject diary recordings.
- Percentage of subjects who demonstrate a response at Week 20 and again at Week 24. A response is defined as the achievement of at least a 20% reduction from baseline (Visit 2) in weekly PN/I.V. volume.
- Change in days per week of PN/I.V. support
- Changes in plasma citrulline levels from baseline to Week 24 (or EOT)

2.2.2 Efficacy and Pharmacodynamic Endpoints – Stages 3 and 4

For Stages 3 and 4, absolute and percent change from baseline in weekly PN/I.V. volume and changes in days per week of PN/I.V. support and plasma citrulline levels will continue to be evaluated throughout the long-term extension.

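### With 9 to 13 of 14 diary days, the weekly PN/IV volume of an intermittent user is imprecise enough to cross the 20% response threshold with PN unchanged, and a baseline on 9 points carries its error to both response visits

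*SAP*

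**What the plan says.** Section 2.2.1 of the SAP bases weekly PN/IV volume on the subject diary. Section 11.1 gives the calculation:

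- The source is the "daily volumes recorded in subjects' diaries within 14 days prior to each scheduled visit".
- The weekly value is "sum of daily values in the diary/number of days with values", multiplied by 7.
- On gaps: "Missing daily PN volumes will not be imputed", and "If there are more than 5 days of missing diary data within an interval, the interval will be classified as missing actual volume information".
- Baseline is an exception. If the window is too sparse, the search goes back more than 14 days before "first dose until 9 data points were obtained".

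The result feeds the response endpoint: "A response is defined as the achievement of at least a 20% reduction from baseline (Visit 2) in weekly PN/I.V. volume". This is tabulated at each visit and in combined form: "The number and percentage of subjects who demonstrate a response at Week 20 and again at Week 24 will be presented". It also feeds the absolute and percent volume change, with 95% confidence intervals at Week 24 and at the end of Stage 2.

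Section 2.2.1 also lists "Change in days per week of PN/I.V. support" as an endpoint, so the plan allows for subjects who do not infuse every day.

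**The concern.** Fourteen complete days contain each weekday twice, so for a fixed weekly schedule the mean times 7 is exactly the weekly volume. Nine to 13 days are generally not a whole number of weeks. For a subject who infuses on only some days, the share of infusion days among the recorded days then depends on which days were lost. This has nothing to do with how PN-free days are coded: it remains when each is entered as 0.

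The endpoint applies a fixed 20% cut to a single subject's value, and section 2.1 plans for at least 5 subjects. With 5 subjects, one misclassification moves the response rate by 1/5 = 20 percentage points. The error works in both directions, so it can also hide a true response. Error at baseline is shared by every later comparison.

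**Working it through.** **Inputs.** From SAP section 11.1: a 14-day window, at most 5 missing days, a multiplier of 7 and a 20% threshold. Assumed, because the SAP gives no figures: k infusion days per week with equal volume each, zeros entered on PN-free days, PN truly unchanged, and days missing at random.

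**The plan's own figure.** 14 - 5 = 9 recorded days, which agrees with the 9 data points required at baseline.

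**Illustration.** 3 L on Monday, Wednesday and Friday is 9 L/week. A diary from Saturday to the second Sunday has 9 days and 3 infusions. The formula gives 9/9 x 7 = 7.0 L, and 7.0/9 - 1 = -22.2%.

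**General formula.** A full window holds 2k infusion days. With m missing days, j of them infusion days, estimate/truth = 7(2k - j) / [(14 - m)k], and j is hypergeometric (14 days, 2k infusion days, m drawn). Since E(j) = 2km/14, the expected ratio is exactly 1, so the estimate is unbiased.

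**False response at one visit, k = 3, complete baseline:**

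- m = 1: the largest fall is 10.3%, so the chance is 0.
- m = 2: both lost days must be infusion days (4/12 x 7 = 2.33 against 3, -22.2%). Chance 15/91 = 16.5%.
- m = 3: all three must be (3/11 x 7 = 1.91, -36.4%; losing two gives only -15.2%). Chance 20/364 = 5.5%.
- m = 4: at least three (3/10 x 7 = 2.10, -30.0%). Chance (160 + 15)/1001 = 17.5%.
- m = 5: at least three (3/9 x 7 = 2.33, -22.2%). Chance (560 + 120 + 6)/2002 = 34.3%.

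The sequence is not monotone because the number of lost infusion days needed to cross 20% moves in whole steps.

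**Other frequencies, complete baseline:**

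| Infusion days/week | m=1 | m=2 | m=3 | m=4 | m=5 | SD of error at m=5 |
|---|---|---|---|---|---|---|
| 3 | 0% | 16% | 5% | 18% | 34% | 24% |
| 4 | 0% | 0% | 15% | 7% | 24% | 18% |
| 5 | 0% | 0% | 0% | 0% | 13% | 13% |
| 6 | 0% | 0% | 0% | 0% | 0% | 8% |
| 7 | 0% | 0% | 0% | 0% | 0% | 0% |

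At 6 days per week the worst case is 7/9 x 7 = 5.44 against 6, or -9.3%.

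**Week 20 and Week 24 together, k = 3.** With 5 days missing at each visit and a complete baseline, 0.343 x 0.343 = 11.7%. If baseline also rests on 9 of 14 days, 18.9%.

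**Baseline alone, k = 3.** Suppose baseline rests on 9 random days of 14 and both later diaries are complete. Five infusions among the 9 give 5/9 x 7 = 3.89, so an unchanged 3 appears as -22.9%; six give 4.67 and -35.7%. The chance is (420 + 56)/2002 = 23.8%, and the false response then appears at both visits. The corresponding figures are 6.3% at k = 4, 0.5% at k = 5 and 0% at k = 6 or 7. For a baseline traced back beyond 14 days this is an approximation.

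**Would weekday-matched averaging be a safe replacement?** It returns 9.0 L in the illustration. It is exact only for fixed-weekday schedules. For an unchanged alternate-day schedule with 2 missing days, among windows where each weekday has at least one entry, the error SD is 20% against 12% for the SAP formula, and the false-response chance is 25% against 0%. Some weekday is also empty in both weeks in 84/364 = 23% of windows with 3 missing days and 1330/2002 = 66% with 5.

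**The case against.** A reader might infer that the formula is biased, or simply does not give a weekly volume. The documents do not support that. Under random missingness it is unbiased. Bias would need gaps that follow infusion or PN-free days, and nothing in the SAP indicates this.

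A reader might also take the 34% at face value as the expected misclassification rate. It is the limit of exactly 5 missing days at 3 infusion days per week. With fewer gaps the chance is mostly much smaller, and one missing day never suffices at 3 or more infusion days per week. The combined endpoint needs the error at both visits or a distorted baseline. Purely as an illustration, if 10% of windows had 5 missing days, independently, the 11.7% would become 0.1 x 0.1 x 11.7% = about 0.1%.

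There is also a real cross-check. Response, by-visit response and volume change are repeated on investigator-prescribed data (Tables 14.2.1.3-4, 14.2.2.3-4 and 14.2.3.3-4), and Listing 16.2.6.5 sets prescribed beside actual support. In a small descriptive study, an unchanged prescription next to a diary response would be visible to someone looking for it.

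All of this stands and limits the point. What it does not remove is that the efficacy endpoint is defined on the diary, the prescribed-data tables do not correct it, and no analysis in section 11.1 shows whether a responder's status depends on an incomplete window. Requiring two visits gives no protection against baseline error.

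**Conclusion.** The point holds as one of precision in individual subjects, not of systematic bias. With 9 to 13 diary days, a subject on 3 to 5 infusion days per week can meet the 20% criterion with PN unchanged. At one visit with a complete baseline, the chance at 3 days per week runs from 0 to 34% according to the number of missing days. At 5 days per week it is 13%, and only at the limit of 5 missing days. At 6 or 7 days per week it is zero.

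The baseline rule is the weaker part, because stopping at 9 points places one error in both response visits: 23.8% at 3 days per week, 0.5% at 5.

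These figures rest on equal volumes, random gaps and recorded zeros. With complete diaries and a fixed weekly schedule, or with equal daily infusions, the error is zero. How often the problem arises cannot be said from the SAP. The change is worth making because it is cheap and the number of subjects is small.

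**What to change.** 1. **Baseline.** When the 14-day baseline window is incomplete, trace back within the stabilization period, under the same stable prescription, until two full weeks of entries are obtained where available: 14 data points with each weekday covered. Do not stop at 9. Section 2.1 requires at least 4 stable weeks, so there is room to do this. State what applies when 14 points cannot be found.
2. **Post-baseline visits.** Keep the stated formula and missing-day limit. Add a sensitivity analysis of response and volume change that uses weekday-matched averages for subjects with a fixed weekday schedule, and for all others only complete 14-day (or complete 7-day) windows. Flag any responder whose status changes, or whose prescribed volume is unchanged.

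Weekday matching should not replace the formula outright, since it enlarges the error for alternate-day schedules.

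Cost: SAP wording and a little extra programming, with no new data collection. Some windows will drop out of the sensitivity analysis. Section 6.4 reports that an interim analysis has taken place; if it used the 9-point baseline, values for the affected subjects may differ from those reported then, and both should be shown.

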11 PHARMACOKINETIC EVALUATION

Details of pharmacokinetic evaluation are included in the Pharmacokinetic Analysis Plan.

12 SAFETY EVALUATION

All safety evaluations will be conducted on the Safety population at the following time points.

- Concomitant medication will be summarized for the study period for all enrolled subjects.
- AEs will be summarized for the study period for all enrolled subjects.
- Vital signs will be summarized at Baseline, Stage 2 Weeks 2, 4, 8, 12, 16, 20, 24, and nominal visits in Stage 3 and Stage 4 will be summarized.
- Electrocardiograms will be summarized at Baseline, Stage 2 Weeks 4, 24, and nominal visits in Stage 3 and Stage 4 will be summarized.
- Lab tests will be summarized at Baseline, Stage 2 Weeks 2, 4, 8, 12, 16, 20, 24, and nominal visits in Stage 3 and Stage 4 will be summarized.
- Antibodies to teduglutide and ECP will be summarized at Baseline, Stage 2 Weeks 12, 24, and nominal visits in Stage 3 and Stage 4 will be summarized.
- 48-hour oral fluid intake and 48-hour urine output will be summarized at Baseline, Stage 2 Weeks 2, 4, 8, 12, 16, 20, 24, and nominal visits in Stage 3 and Stage 4 will be summarized.
- Body weight and BMI will be summarized at Baseline, Stage 2 Weeks 2, 4, 8, 12, 16, 20, 24, and nominal visits in Stage 3 and Stage 4 will be summarized.

Complete dates will be imputed from partial dates of adverse events and medications solely for the purpose of defining treatment emergence for adverse events and prior/concomitant status for medications. Dates will be defined using the hierarchy of derivations below.

Adverse event or medication start date (references to month are the month of the start date):

1. If year and month are known, and it is the month and year of the first dose date, use the first dose date.
2. If year and month are known, and it is the month and year of the informed consent, use the informed consent date.
3. If year and month are known, and the month is not the month and year of the first dose or informed consent, use the first day of the month.
4. If only year is known, and it is previous to the year of the informed consent, use June 30th of that year.
5. If only year is known, and it is the year of the informed consent, use the informed consent date.
6. Should any of the previous start dates created be after a complete stop date provided, use the stop date instead of the date that would otherwise be created.
7. Otherwise, if start date is unknown leave as missing.

Medication stop date (references to month are the month of the stop date):

1. If year and month are known and study medication stopped during that month and year, use the stop date of study medication.
2. If year and month are known and informed consent was provided during that month and year, use the date of informed consent.
3. If year and month are known and study medication stopped after the date of informed consent and not in the month that medication stopped, use the last day of the month.
4. If year and month are known and are prior to the month of informed consent, use the first day of the month.
5. If only year is known and study medication stopped during that year, use the stop date of study medication.

6. If only year is known and study medication stopped after that year, use December 31st of that year.
7. If only year is known and study medication stopped prior to that year, use the first day of the year.
8. Should any of the previous stop dates created be before a start date, either a complete date or an imputed one, use the (imputed) start date instead of the date that would otherwise be created.
9. Otherwise, if stop date is unknown leave as missing.

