1 INTRODUCTION AND BACKGROUND INFORMATION

2.1 Study Design

This is an open-label, multicenter, 4-stage study consisting of an optimization/stabilization period (Stage 1), a 24-week treatment period in which all subjects will receive teduglutide 0.05 mg/kg/day (Stage 2), and a long-term extension (Stages 3 and 4).

At least 5 subjects may be enrolled during the recruitment period, which ends approximately 6 months after the initiation of the study.

Main Treatment Period (Stages 1 and 2)

Stage 1 will include a screening visit; a maximum 8-week PN/I.V. optimization period (if required); and a stabilization period that demonstrates stable PN/I.V. support for a minimum of 4 weeks to a maximum of 8 weeks.

If at screening a subject does not have a stable PN/I.V. volume, defined as a 48-hour urine output within 2 to 4 L, he/she will enter the optimization period, during which the minimally tolerated stable PN/I.V. volume will be determined during a period of up to 8 weeks. If it is not possible to keep the subject adequately hydrated and nourished within the target urine output range, the minimally tolerated PN/I.V. volume will be documented.

All subjects will then enter the stabilization period, during which the target volume will be maintained for at least 4 consecutive weeks (8 weeks maximum) prior to entering the dosing period (Stage 2).

If a subject fails to maintain a stable PN/I.V. volume for at least 4 consecutive weeks, the subject may start the optimization period again, beginning with Week 2 (Visit 1.1). Those subjects who fail to stabilize after 2 attempts will not proceed further and will not be included in Stage 2.

Stage 2 will be a 24-week dosing period, during which subjects will self-administer teduglutide 0.05 mg/kg/day at home. Stage 2 will begin with baseline assessments of hydration and nutritional status once the subjects have demonstrated PN/I.V. stability for 4 to 8 weeks. At least 5 subjects will be enrolled. The on-treatment study visits will occur at Weeks 2, 4, 8, 12, 16 and 20, with the last scheduled visit at Week 24 of Stage 2.

Extension Treatment Period (Stages 3 and 4)

[figure not shown]

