5 STATISTICAL/ANALYTICAL ISSUES

6.1 General Methodology

All statistical procedures will be completed using SAS version 9.2 or later.

The small sample size resulting from the small study population requires the use of descriptive statistics with a goal of summarizing the sample and thus discourages the use of inferential statistics. Continuous variables, including those assessed on a discrete scale, will be summarized using descriptive statistics including number of subjects, mean, median, standard deviation, maximum, and minimum. For categorical variables, statistical summaries will include number of subjects and percentages.

For summary purposes, the baseline value will be defined as the last available pre-dose value. Scheduled visits will be summarized as provided in the electronic case report forms (eCRFs). An End of Treatment (EOT) time point, defined as the last determination of endpoint or last available measurement from the date of first dose, will be analyzed in addition to the scheduled visits.

Study Day will be calculated as the date of the evaluation minus the date of the first day of study medication for study days before the first day of study medication, and the date of the evaluation minus the date of the first day of study medication plus one otherwise.

All summaries will be presented by one group, unless otherwise specified. Subjects in the eCRF database who were not treated with study medication will be included in the disposition table as “Enrolled”. For subject data listings, these subjects will be listed in a treatment group specified as ‘Not Treated’.

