6 ANALYSIS POPULATIONS AND VISITS

7.1 Efficacy/PD Analysis Populations

The intention-to-treat (ITT) population will consist of all subjects who are enrolled and eligible to enter Stage 2. The ITT population will be the primary analysis population analyzed for efficacy/PD endpoints.

The Per Protocol population will consist of all subjects in the ITT population who completed Stage 2 without any major protocol violations that could potentially affect the efficacy conclusions of the study. The major protocol violations will be determined with the following conditions, but not limited to:

1. Subjects with no detectable TED level in blood as part of PK assessment or no PK assessment.
2. Absence of Week 20 and Week 24 visits
3. Non-compliance to study medication for the treatment group

Compliance is defined in Section 9.
4. Discrepancies between planned and actual treatment

The Per Protocol (PP) population will be the secondary analysis population analyzed for efficacy endpoints.

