7.2 Safety Analysis Population

The Safety Population will consist of all subjects in the ITT population who receive at least one dose of study medication. All safety analyses will be conducted on this population, unless otherwise specified.

All data will be included in the listings.

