8.4 Disposition of Subjects

For the ITT and Safety populations, study enrollment and completion will be summarized by the number and percent of subjects who complete Stages 2, Stage 3, Stage 3 V7 and Stage 4. The number and percent of subjects by the reason for discontinuing each stage early will also be presented.

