| Table 14.3.2.13.1 | Details of Adverse Events Leading to Discontinuation - Stage 2 Only | Safety Population |
| Table 14.3.2.13.2 | Details of Adverse Events Leading to Discontinuation - Stage 3 and 4 Only | Safety Population |
| Table 14.3.2.14 | Details of Adverse Events Leading to Death | Safety Population |
| Table 14.3.2.14.1 | Details of Adverse Events Leading to Death - Stage 2 | Safety Population |
| Table 14.3.2.14.2 | Details of Adverse Events Leading to Death - Stage 3 and 4 Only | Safety Population |
| Table 14.3.2.15 | Summary to Treatment Emergent Adverse Events by Time to Onset, System Organ Class, and Preferred Term | Safety Population |
| Table 14.3.2.16 | Summary of Pre-treatment Adverse Events by System Organ Class and Preferred Term | Safety Population |
| Table 14.3.2.17 | Summary of Treatment Emergent Central Line Systemic Infections by Preferred Term | Safety Population |
| Table 14.3.2.17.1 | Summary of Treatment Emergent Central Line Systemic Infections by Preferred Term - Stage 2 Only | Safety Population |
| Table 14.3.2.17.2 | Summary of Treatment Emergent Central Line Systemic Infections by Preferred Term - Stage 3 and 4 Only | Safety Population |
| Table 14.3.3.1 | Summary of Laboratory Values and Change from Baseline by Visit - Chemistry | Safety Population |
| Table 14.3.3.2 | Summary of Laboratory Values and Change from Baseline by Visit - Hematology | Safety Population |
| Table 14.3.3.3 | Summary of Laboratory Values and Change from Baseline by Visit - Urinalysis | Safety Population |
| Table 14.3.3.4 | Summary of Antibody Results by Visit | Safety Population |
| Table 14.3.3.5 | Shift from Baseline to Post-baseline in Clinical Laboratory Parameters by Visit - Chemistry | Safety Population |
| Table 14.3.3.6 | Shift from Baseline to Post-baseline in Clinical Laboratory Parameters by Visit - Hematology | Safety Population |
| Table 14.3.3.7 | Shift from Baseline to Post-baseline in Clinical Laboratory Parameters by Visit - Urinalysis | Safety Population |
| Table 14.3.3.8 | Summary of Post-Baseline Markedly Abnormal Laboratory Values – Chemistry | Safety Population |
| Table 14.3.3.9 | Summary of Post-Baseline Markedly Abnormal Laboratory Values – Hematology | Safety Population |
| Table 14.3.4.1 | Change and Percent Change in 48-hour Fluid Intake from Baseline by Visit | Safety Population |
| Table 14.3.4.2 | Change and Percent Change in 48-hour Urine Output from Baseline by Visit | Safety Population |

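### The SAP contradicts itself on how subjects who leave in Stage 1 are summarized: the pre-treatment AE table omits them, and no table gives Stage 1 completion or reasons for leaving.

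*SAP*

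**What the plan says.** **Adverse events.** Section 12 opens with "All safety evaluations will be conducted on the Safety population at the following time points". A bullet directly below says "AEs will be summarized for the study period for all enrolled subjects". Section 13.2 plans a summary of pre-treatment events without naming a population. Section 16.1 lists Table 14.3.2.16, "Summary of Pre-treatment Adverse Events by System Organ Class and Preferred Term", and assigns it to the Safety Population.

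**Disposition.** Section 6.1 says "Subjects in the eCRF database who were not treated with study medication will be included in the disposition table as" Enrolled. Section 8.4 says "For the ITT and Safety populations, study enrollment and completion will be summarized by the number and percent of subjects who complete Stages 2", followed by Stage 3, Stage 3 V7 and Stage 4, with reasons for early discontinuation of each stage. Section 16.1 lists two disposition tables: 14.1.2.1 on ITT and 14.1.2.2 on Safety.

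**Populations.** Section 7.1: "The intention-to-treat (ITT) population will consist of all subjects who are enrolled and eligible to enter Stage 2". Section 7.2: "The Safety Population will consist of all subjects in the ITT population who receive at least one dose of study medication". Section 2.1, on Stage 1: "Those subjects who fail to stabilize after 2 attempts will not proceed further and will not be included in Stage 2".

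**The concern.** Stage 1 is more than a screening visit. Section 2.1 describes up to 8 weeks of adjusting PN/I.V. volume where needed, then 4 to 8 weeks of stabilization, and a second attempt is allowed. Section 2.2.4 places any colonoscopy or sigmoidoscopy not recently done, and an upper GI contrast series for subjects with a history of Crohn's disease, in the stabilization period.

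The SAP considers events before dosing worth a table of their own. On the Safety Population, that table describes only subjects who went on to be dosed. An event that ended participation in Stage 1 cannot enter it. Likewise, the stability run-in selects the efficacy population, but no planned table says how many completed it or why the others left.

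A programmer also cannot follow both halves of Section 12, and cannot readily follow Section 6.1 together with Section 8.4. The choice would be made at programming, without a rule.

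**Working it through.** No sample size, power or test is at issue, and the plan states no figure to reproduce. The check compares population definitions with the population named for each output.

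**Step 1: nesting.** By Section 7.2, Safety is part of ITT. By Section 7.1, ITT is part of Enrolled, with eligibility for Stage 2 as a further condition. So Safety ⊆ ITT ⊆ Enrolled.

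**Step 2: where a Stage 1 leaver falls.** Section 2.1 bars a subject who does not stabilize from Stage 2. That subject is not in ITT, and therefore not in Safety. A subject who qualifies for Stage 2 but leaves before the first dose is in ITT but not in Safety.

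**Step 3: which outputs can contain each subject.**

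| Output | Population | Stage 1 failure | Eligible, never dosed |
|---|---|---|---|
| Table 14.3.2.16, pre-treatment AEs | Safety | no | no |
| Table 14.1.2.1, disposition | ITT | no | yes |
| Table 14.1.2.2, disposition | Safety | no | no |
| Table 14.1.1, analysis populations | All enrolled | yes, as a count | yes, as a count |
| Listings 16.2.1, 16.2.7.1, 16.2.7.2 | All enrolled | yes | yes |

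**Step 4: against the text.** The Section 12 bullet promises an AE summary for all enrolled subjects, but every AE summary in Section 16.1 is on Safety. Section 6.1 promises untreated subjects in the disposition table, but neither disposition population admits a Stage 1 failure. The section on changes from the protocol lists three changes, and none concerns this.

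**Step 5: what can be recovered.** Section 8.1 gives the numbers enrolled and treated. Section 8.2 and Table 14.1.1 give the ITT and Safety counts. Hence:
- enrolled − ITT = subjects who did not qualify for Stage 2
- ITT − Safety = subjects who qualified but were never dosed

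Reasons for the first group's departure are in Listing 16.2.1 only.

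**Step 6: possible size.** The SAP gives no number of Stage 1 leavers, so the counts below are assumptions. With 5 treated subjects and k leavers, the share reaching treatment is 5/(5 + k):
- k = 0: 5/5 = 100%
- k = 1: 5/6 = 83.3%
- k = 2: 5/7 = 71.4%
- k = 3: 5/8 = 62.5%

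The Safety disposition table shows 5 subjects in every case.

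For Table 14.3.2.16, suppose 1 of the 5 dosed subjects had a pre-treatment event, so the table shows 1/5 = 20%. With k = 2, the all-enrolled figure is:
- neither leaver had an event: 1/7 = 14.3%
- one had: 2/7 = 28.6%
- both had: 3/7 = 42.9%

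The figure can move either way. In time, one Stage 1 attempt can last 8 + 8 = 16 weeks, against 24 weeks for Stage 2.

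**The case against.** The other side has a good case on consequence.

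- A reader might infer that attrition is hidden. It is not: Table 14.1.1 is on all enrolled subjects and, with Sections 8.1 and 8.2, shows the number lost before dosing. This stands.
- A reader might infer that run-in harm goes unreported. Listings 16.2.7.1 and 16.2.7.2 cover all enrolled subjects, and Section 13.2 flags events that are not treatment-emergent. In a study of this size they can be read line by line. This stands, so the point concerns the summary tables only.
- A reader might infer that early leavers are the subjects most likely to have had events. The SAP describes leaving for an unstable PN/I.V. volume and says nothing about event rates. This stands, and the 14.3% to 42.9% range shows that the direction is open.
- Treatment-emergent events require a dose, so no treatment-emergent or efficacy table is affected. This stands.
- The disposition tables might carry an added row for untreated subjects, and the shells are in a separate file. This is possible, but a table labelled ITT or Safety would then count subjects outside its own population. Section 6.1 also asks only that these subjects appear as enrolled, so showing Stage 1 reasons is a recommendation beyond its text.
- The SAP does not define enrolled, and the protocol may. Even so, Section 7.1 adds eligibility as a separate condition and Section 6.1 applies the word to untreated subjects, so it must reach beyond those treated.
- Section 7.2 allows exceptions to the Safety population, so the AE bullet could be one. No listed AE table carries that exception out.

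**Conclusion.** Both contradictions are established from the SAP's own definitions. As listed, Table 14.3.2.16 leaves out events in subjects who left before dosing, against the Section 12 bullet. The two disposition tables leave out Stage 1 failures, against Section 6.1, and Stage 1 completion and reasons for leaving are not tabulated.

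The reach is one AE table and the disposition tables. The documents do not support a claim that attrition is concealed or that safety data are lost, because counts can be derived and individual records are listed. The size depends on the number of Stage 1 leavers and their events, which the SAP does not give. With no leavers the effect is nil. With a minimum of 5 subjects, one or two leavers would visibly change the percentages. The conclusion assumes that subjects in Stage 1 count as enrolled, which Sections 6.1 and 7.1 imply. The change should be made, though it does not bear on the main conclusions of the study.

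**What to change.** 1. Assign Table 14.3.2.16 to All Enrolled Subjects.
2. In Section 12, limit the opening Safety-population sentence to on-treatment evaluations, and state that pre-treatment events are summarized for all enrolled subjects. The bullet on concomitant medication has the same all-enrolled wording, while Table 14.1.9.2 is on Safety, so settle it in the same edit.
3. Put one disposition table on All Enrolled Subjects (for example, change Table 14.1.2.1), with the number leaving in Stage 1 and the reason, including failure to stabilize.
4. Amend Section 8.4 to agree with Section 6.1.

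The cost is a few sentences of SAP text and minor reprogramming of two tables. The data are already planned for Listings 16.2.1 and 16.2.7.1, so nothing new is collected and no trial procedure changes. The downside is that the reported counts may look less favourable.
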